7 STUDY ASSESSMENTS AND PROCEDURES

7.1 ADVERSE EVENTS AND SERIOUS ADVERSE EVENTS

7.1.1 DEFINITION OF ADVERSE EVENTS

Any untoward medical occurrence, unintended sign, symptom, illness or disease temporally associated with the study protocol regardless of the suspected cause.

7.1.2 DEFINITION OF SERIOUS ADVERSE EVENTS

An Adverse Event that is considered "serious" if it meets at minimum one of the three Seriousness reporting criterions below:

1. Led to death,
2. Led to a serious injury which:
 - a. Resulted in a life-threatening illness or injury, or
 - b. Resulted in a permanent impairment of a body structure or a body function, or
 - c. Resulted in medical or surgical intervention to prevent life-threatening illness or injury or permanent impairment to a body structure or a body function

7.1.2.1 RELATIONSHIP TO STUDY INTERVENTION/EXPERIMENTAL MANIPULATION

All AEs will be assessed for relationship to the study protocol based on the following definitions:

Not Related: There is no clear evidence that the AE has a relationship to the study protocol and can be attributed to an underlying or concurrent illness/clinical condition or an effect of another device, drug or treatment.

Related: There is a clear causal relationship of the AE to the marketed device or procedure beyond reasonable doubt.

7.1.3 TIME PERIOD AND FREQUENCY FOR EVENT ASSESSMENT AND FOLLOW-UP

All enrolled subjects will be monitored for adverse events by review of the medical record on a monthly basis by [name]. Subjects will have routine follow up scheduled 10 days postoperatively at which time in-person visit will be performed and assessment of adverse events may be performed.

7.1.4 ADVERSE EVENT REPORTING

Adverse events must be reported to the IRB as soon as possible and no later than **2 working days** after the PI first becomes aware of the event. The PI or designee must record all AE information that can be gathered within the reporting timeframe and enter it onto the AE eCRF.

Relevant follow-up information should be submitted to the IRB as soon as it becomes available and/or upon request.

7.1.5 SERIOUS ADVERSE EVENT REPORTING

See section 7.1.4

7.1.6 REPORTING EVENTS TO PARTICIPANTS

All SAE's or AE's will be reported to affected participants by the principal investigator directly.

8 STATISTICAL CONSIDERATIONS

8.1 STATISTICAL HYPOTHESES

After sufficient patient enrollment and specimen collection, all the samples will be analyzed for kidney and urothelial injury biomarkers using urinary assays (ELISA, CLIA, etc.). The biomarkers that will be qualified and quantified in the urine include Cystatin C, Kidney Injury Molecule-1 (KIM-1), Neutrophil gelatinase-associated lipocalin (NGAL), Beta-2-microglobulin, Microalbumin urine, spot creatinine, total protein, and glycosaminoglycans.

Abundance of each kidney injury biomarker for each laser will be analyzed using the Kruskal-Wallis statistical test. Multiple multivariate regression will also be used to control for stone size, operative time, and other potential confounders.

8.2 SAMPLE SIZE DETERMINATION

A sample size of 108 patients will be accrued locally. We are enrolling 108 patients to allow for any potential exclusions due to failure to follow up or for patients who were not stented.

A study by Fahmy et al. prospectively evaluated urinary Kidney Injury Marker-1 (uKIM-1) levels in patients undergoing kidney stone surgery to compare the effect of Extracorporeal Shockwave Lithotripsy (ESWL) and Ureteroscopy/Laser Lithotripsy (URS) on biomarkers of renal damage¹. In this study, the 50 patients in the ESWL arm had a mean preoperative uKIM-1 of 5.78ng/mL (SE=0.8) and the 10 patients in the URS arm similarly had a mean preoperative uKIM-1 of 5.78ng/mL (SE=2.0). Two hours post operatively, the ESWL group had a mean uKIM1 of 10.14ng/mL (SE=1.4) and the URS group had a uKIM-1 of 5.49ng/mL (SE 0.7, SD=2.21). Another study by Timmeren et al evaluated uKIM1 in 11 health controls and 53 patients with varying degrees of kidney disease and found a -0.37 correlation ($p=0.016$) between uKIM-1 levels and eGFR.² That is, a 1ng/mL rise in uKIM1 correlated to a 0.37mL/min decline in eGFR. The purpose of our statistical analysis is to evaluate for non-inferiority of the two laser modalities in regard to occult kidney damage. Given that kidney stone disease is a recurrent illness often requiring multiple surgical interventions over the course of a patient's lifetime, we defined non-inferiority as producing a change in eGFR 1mg/mL. With an allocation ratio of 1:1, 99% power, non-inferiority limit of 40%, and alpha of 5%, using the noninferiority power calculation, our sample size is 49 patients in each study arm for 98 patients in total (~100). Based on these calculations and factoring in a 10% dropout rate, we seek to enroll 108 total patients.

Power Calculation References

2. van Timmeren MM, van den Heuvel MC, Bailly V, Bakker SJ, van Goor H, Stegeman CA. Tubular kidney injury molecule-1 (KIM-1) in human renal disease. *The Journal of pathology*. 2007;212(2):209-217.

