1.3 SCHEDULE OF ACTIVITIES

After randomization, the patient will undergo URS using either the Thulium or Hol:YAG laser. Both lasers are used as part of the standard of care and are used interchangeably. At the beginning of all procedures, the surgeon will empty the bladder and collect a 2 mL sample of urine that will serve as the “Preoperative Urine Sample”. It is the standard of care to collect urine at the beginning of the surgery to send to pathology. The only deviation is that a portion of the urine will be for research. One hour following the end of the procedure, a member of [name] research team will collect a second 2 mL sample of urine that will serve as the “Immediate Post-Op Urine Sample”. This will be collected using the catheter that was placed during surgery. If no catheter was placedb the patient will provide the urine sample.

After collection, the samples will be subsequently frozen in a freezer at -80 °C freezer operated by the pathology department at Mount Sinai West hospital.

A third and final sample of urine will be collected at the patients’ 10-day follow up appointment for stent removal which will serve as the “Follow-up Urine Sample”. To standardize the duration in which the last urine samples are collected, only patients who have been stented will be included in the study, as standard of care for stent removal is ten days. Upon receiving the third and final specimen 10 days postoperatively, the subject’s enrollment will be considered complete. All procedures and appointments are the standard of care.

After sufficient patient enrollment and specimen collection, all the samples will be analyzed for kidney and urothelial injury biomarkers using urinary assays (ELISA, CLIA, etc.). The biomarkers that will be qualified and quantified in the urine include Cystatin C, Kidney Injury Molecule-1 (KIM-1), Neutrophil gelatinase-associated lipocalin (NGAL), Beta-2-microglobulin, Microalbumin urine, spot creatinine, total protein, and glycosaminoglycans.

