5 STUDY INTERVENTION(S) OR EXPERIMENTAL MANIPULATION(S)

5.1 STUDY INTERVENTION(S) OR EXPERIMENTAL MANIPULATION(S) ADMINISTRATION

5.1.1 STUDY INTERVENTION OR EXPERIMENTAL MANIPULATION DESCRIPTION

For subjects receiving URS, randomization will occur preoperatively. These subjects will be randomized to undergo lithotripsy with either Ho:YAG or TFL lasers (100 subjects in each arm).

All subjects will undergo surgical interventions that abide by broadly accepted guidelines and standards of care, allowing for slight variations in technique as seen necessary by the attending surgeon [name].

The type of laser that is chosen in SOC is based on hospital availability. That is, most hospitals only have one laser type to choose from (and that laser type is generally contingent on the biomedical contracts the hospital holds with the various laser manufacturers). We are uniquely situated at Mount Sinai West in that we have multiple laser systems to choose from. Multiple surgeons share the lasers, and typically [name] will use whichever laser is already in the room or readily available. Approximately 50% of ureteroscopies were performed with each laser, +/- 10%.

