8.4.2 ANALYSIS OF THE PRIMARY ENDPOINT(S)

Abundance of each kidney injury biomarker for each laser will be analyzed using the Kruskal-Wallis statistical test. Multiple multivariate regression will also be used to control for stone size, operative time, and other potential confounders.

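### Section 8.2 reads a unitless correlation as an eGFR slope and does not connect it to the 40% limit used; section 8.4.2 compares nothing with a margin, and section 5.1.1 contradicts the total of 108

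*Combined protocol and SAP*

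**What the plan says.** Section 8.2 takes two facts from cited studies. The first is uKIM-1 in 10 ureteroscopy patients: mean 5.78 ng/mL (SE 2.0) before surgery, and 5.49 ng/mL (SE 0.7, SD 2.21) two hours after it. The second is a correlation of -0.37 between uKIM-1 and eGFR, which the plan interprets as follows: "That is, a 1ng/mL rise in uKIM1 correlated to a 0.37mL/min decline in eGFR".

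The section then gives the aim: "The purpose of our statistical analysis is to evaluate for non-inferiority of the two laser modalities in regard to occult kidney damage". It defines the criterion on the eGFR scale: "we defined non-inferiority as producing a change in eGFR 1mg/mL". The calculation itself uses a different quantity: "With an allocation ratio of 1:1, 99% power, non-inferiority limit of 40%, and alpha of 5%, using the noninferiority power calculation". The result is 49 per arm, 98 in total, and 108 after allowing for dropout.

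Section 8.4.2 plans the primary analysis: "Abundance of each kidney injury biomarker for each laser will be analyzed using the Kruskal-Wallis statistical test". It adds regression to control for confounders. Section 8.1 says the same. The objectives and endpoints, in the synopsis and in the objectives table, ask whether laser type predicts differences in biomarkers or is associated with renal damage.

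On size, section 5.1.1 says "These subjects will be randomized to undergo lithotripsy with either Ho:YAG or TFL lasers (100 subjects in each arm". Section 5.3 assigns subject IDs 1 to 108 with equal allocation, section 8.2 enrols 108 in total, and the synopsis anticipates 100.

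**The concern.** The correlation-as-slope sentence is the only bridge from uKIM-1 to kidney function. If it fails, the eGFR definition cannot justify any margin in ng/mL or per cent, and a reader cannot tell which margin the trial would be judged against.

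Separately, a non-inferiority conclusion needs an estimate and interval set against a margin fixed in advance. If the only formal comparison is a test of no difference, a non-significant result may be taken as reassurance that it does not give, and a significant one may be read as harm although the difference lies inside the limit. A margin chosen after the data are seen would not be credible, so the gap has to be closed before analysis.

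**Working it through.** **1. Reproducing the plan's 49 per arm.** The formula, scale and sidedness are not stated, so variants were tried with the section 8.2 inputs: mean 5.49, SD 2.21, limit 40%, power 99%, alpha 5%.

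- Ratio scale: CV = 2.21/5.49 = 0.4026; log-scale SD s = √ln(1 + 0.4026²) = 0.3875; d = ln 1.40 = 0.3365. Then n per arm = 2(1.960 + 2.326)²(s/d)² = 48.7, so 49. This is two-sided 5% (one-sided 2.5%).
- Raw scale: d = 0.40 × 5.49 = 2.196 ng/mL gives 37.2, so 38 (two-sided 5%), or 32 (one-sided 5%).

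The ratio route matches exactly. It uses neither eGFR nor 0.37.

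**2. Correlation against slope.** A regression slope is r × SD(eGFR)/SD(uKIM-1). It equals 0.37 in size only if that ratio of SDs is exactly 1 mL/min per ng/mL, and the documents give neither SD. For illustration, assumed SD ratios of 0.5, 1, 2 and 4 give slopes of 0.185, 0.37, 0.74 and 1.48, so 1 mL/min would correspond to 5.41, 2.70, 1.35 and 0.68 ng/mL.

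**3. The plan's own reading, taking the printed unit as mL/min.**

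| Starting point | uKIM-1 (ng/mL) | Share of cited mean | eGFR (mL/min) |
|---|---|---|---|
| eGFR change of 1 | 1/0.37 = 2.70 | 49% of 5.49; 47% of 5.78 | 1 |
| 40% of 5.49 | 2.20 | 40% | 2.196 × 0.37 = 0.81 |
| 40% of 5.78 | 2.31 | 40% | 2.312 × 0.37 = 0.86 |

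The 40% limit is the stricter of the two, but no step leads from one to the other.

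**4. What the planned test does.** Kruskal-Wallis was simulated with log-normal data, 49 per arm and 10,000 runs per setting, at the plan's SD (s = 0.3875). A true ratio of 1.20, inside the 40% limit, was significant in 61% of trials; a repeat with 20,000 runs gave 62%. So the test would often flag a difference that the limit allows. In the other direction, a true ratio of 1.40, exactly at the limit, was non-significant in 1.5% of trials at this SD.

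**5. Sensitivity of power to the SD (illustrative).** The cited pre-operative SDs follow from SE × √n: 0.8 × √50 = 5.66 (shockwave group) and 2.0 × √10 = 6.32 (ureteroscopy group). Power = Φ(d/(s√(2/49)) − 1.960), with no true difference, ratio 1.40, two-sided 5% and no baseline adjustment:

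- SD 2.21: 99.0%.
- SD 5.66: s = 0.820 (mean 5.78) or 0.851 (mean 5.49), power 53% or 50%.
- SD 6.32: s = 0.887 or 0.919, power 47% or 44%.

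Baseline adjustment would raise these figures. The documents give no pre/post correlation. At an assumed correlation of 0.7 the range becomes 72-81%.

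**6. Size.** Section 5.1.1: 2 × 100 = 200. Sections 5.3 and 8.2: 108, or 108/2 = 54 per arm with equal allocation.

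**The case against.** Non-inferiority appears only in section 8.2. The objectives, the endpoints and sections 8.1 and 8.4.2 are about differences or association, and Kruskal-Wallis suits that aim. This stands. The defect is that section 8.2 disagrees with the rest of the plan, and keeping the difference aim is a legitimate repair.

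Section 8.4.2 also plans regression, which yields a laser effect and an interval. True, but nothing says that the interval will be compared with a margin, for which biomarker, or at which sample. What is missing is the decision rule.

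The mismatch in margins is conservative, since 40% is tighter than 47-49%. That is correct on the plan's own reading, but that reading rests on the invalid slope.

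A reader might infer that 49 per arm is miscalculated, or that 99% power is disproved. The documents support neither. The 49 reproduces on the ratio scale, and the 44-53% figures apply pre-operative SDs, one of them from shockwave patients, to a post-operative comparison. A milder caveat remains: SD 2.21 comes from 10 patients, and the cited values were taken later than this trial's immediate sample ("Two hours post operatively, the ESWL group had a mean uKIM1 of 10.14ng/mL (SE=1.4) and the URS group had a uKIM-1 of 5.49ng/mL", against "One hour following the end of the procedure" in section 1.3).

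A reader might also take the 200 against 108 as real doubt about the size of the trial. Sections 5.3 and 8.2 agree on 108, and the synopsis figure of 100 is close to the rounded 98, so section 5.1.1 looks like a slip.

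**Conclusion.** The point holds, and the aim, the margin and the decision rule need to be settled before analysis.

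- The eGFR definition has no valid link to uKIM-1, because a correlation is used as a slope. On the plan's own reading it implies 2.70 ng/mL, against 2.20-2.31 ng/mL for the 40% limit, and nothing connects them. This assumes that the printed mg/mL means mL/min.
- As written, no planned result can support the non-inferiority conclusion named in section 8.2. A non-significant Kruskal-Wallis result cannot show it. A significant one is likely (about 60%) at a true ratio of 1.20 under log-normal data, SD 2.21 and 49 per arm.
- The 100 per arm in section 5.1.1 contradicts 108 in total and needs only an editorial correction.

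The sample size is under-documented: scale, sidedness, reference mean and reference laser are not stated.

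**What to change.** (a) **Section 8.2.** Delete the slope sentence and the eGFR definition, or replace them with a sourced regression slope in correct units.

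(b) **Choose one aim** and use it in section 8.2, section 8.4.2 and the objectives.

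- *Option A, non-inferiority or equivalence.* Name one primary biomarker (section 8.2 is built on uKIM-1), one post-operative sample, the reference laser (or a margin in both directions), the alpha with its sidedness, and a justified margin on a stated scale. That 40% returns 49 per arm does not justify it. Add to section 8.4.2: *The confidence interval for the laser effect, on the scale of the margin and adjusted for the pre-operative value, will be compared with the margin; Kruskal-Wallis results are supportive.*
- *Option B, difference.* Remove the non-inferiority statements and the 40% limit from section 8.2, restate the detectable difference and power for 49 evaluable patients per arm, and say that a non-significant result will not be read as non-inferiority.

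(c) **Power, under option A with a ratio of 1.40.** State: *99% power with 49 evaluable per arm assumes no true difference, two-sided 5%, no baseline adjustment and SD 2.21 (10 patients, two hours post-op).* The 44-53% sensitivity range supports this wording but does not belong in the protocol.

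(d) **Section 5.1.1, and the synopsis for consistency.** *108 enrolled in total, 54 per arm.*

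**Cost.** The eGFR interpretation is lost or must be re-sourced, the stated power becomes conditional, and the sponsor must commit to one aim. No extra patients are needed if power is restated; holding it at 99% under a new margin or a larger SD could need more.

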Description of Study Intervention/Experimental Manipulation:	Describe the study intervention (a.k.a, experimental manipulation; hereafter referred to as “study intervention”). Include intervention dose (length and frequency) and how it will be administered. Include method of delivery (e.g., group vs. individual, web-based, etc.).
	Subjects enrolled will undergo surgical treatment of their kidney stones with URS based on clinician judgement and urologic guidelines. Once enrolled, patients will be randomized into one of two groups based on the type of laser used to break apart the stones: Thulium Laser or Hol:YAG Laser. Both lasers are used routinely and interchangeable for this procedure according to the standard of care. The only involvement of patients will be collection of urine samples before and after surgery.
Study Duration * :	Estimated time (in months) from when the study opens to enrollment until completion of data collection.
	12-18 months
Participant Duration:	Time (e.g., in months) it will take for each individual participant to complete all study-related tasks.
	10 days

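### Section 8.2 claims non-inferiority of the two lasers without naming a reference or a direction, and the planned Kruskal-Wallis test cannot support that claim; the power cost of fixing this is small

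*Combined protocol and SAP*

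**What the plan says.** Section 8.2 gives the aim of the analysis: "The purpose of our statistical analysis is to evaluate for non-inferiority of the two laser modalities in regard to occult kidney damage". The limit is first put on the eGFR scale, "we defined non-inferiority as producing a change in eGFR 1mg/mL", with no sign and no statement of which laser is judged against which. The sizing follows: "With an allocation ratio of 1:1, 99% power, non-inferiority limit of 40%, and alpha of 5" per cent, "using the noninferiority power calculation", leading to 49 per arm, 98 in total and 108 enrolled. The sidedness of alpha and the base of the 40% are not given.

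No section calls either laser the control or the reference. The synopsis says "Both lasers are used routinely and interchangeable for this procedure according to the standard of care", sections 1.3, 2.3.1 and 3.2 say much the same, and section 2.1 counts both Thulium and Moses holmium among the newer technologies. The primary objective asks whether laser type predicts differences in biomarkers. Sections 8.1 and 8.4.2 analyse each biomarker by Kruskal-Wallis, with regression to adjust for confounders. Neither section mentions a margin, a confidence interval or a direction.

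**The concern.** Non-inferiority is a claim about a test treatment against a named reference. Without the reference, the aim in 8.2 can be read in three ways: Thulium is not worse than holmium, holmium is not worse than Thulium, or neither is worse than the other. These need different decision rules, and the third needs both one-sided comparisons to succeed. Adding a margin test to 8.4.2 would not settle which is meant.

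What is at stake is the conclusion the trial may draw. Two reports would go beyond the evidence: one that takes success in a single direction as a statement about both lasers, and one that takes a non-significant Kruskal-Wallis result as showing the lasers do equal harm. The plan rules out neither. If the direction is chosen after the biomarkers have been read, the choice will not be credible.

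**Working it through.** **Inputs, all from 8.2 unless marked.** URS post-operative uKIM-1: mean 5.49, SD 2.21 ng/mL. Limit 40%, alpha 5%, power 99%, allocation 1:1, n = 49 per arm. Assumptions: true difference 0, alpha one-sided 5%, and 40% taken of the post-operative mean, so the margin is m = 0.40 × 5.49 = 2.196 ng/mL.

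**1. The plan's own figure.** For means, n per arm = 2·[SD·(z_alpha + z_power)/m]².
- One-sided 5%: 2·[2.21 × (1.645 + 2.326)/2.196]² = 31.9, so 32.
- One-sided 2.5%: 2·[2.21 × (1.960 + 2.326)/2.196]² = 37.2, so 38.

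Neither gives 49. Taking 40% of 5.78 gives 29 or 34, and 1/0.37 = 2.70 ng/mL gives 22 or 25. A formula for proportions with a 40-point margin comes close, but only with an event rate that the plan does not contain: an assumed 50% at one-sided 5% gives 49.28, and an assumed 30% at one-sided 2.5% gives 48.2, rounded up to 49. So 49 does not follow from the stated uKIM-1 inputs, and it does not reveal which sidedness was used. Every variant here that comes near 49 is a one-way formula.

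**2. Power for both directions.** With k = m/[SD·√(2/n)], one-way power is Φ(k − 1.645). Two-way power (two one-sided tests) is 2Φ(k − 1.645) − 1.

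| Basis, 49 per arm | k | One-way | Two-way |
|---|---|---|---|
| Stated 99% taken at face value (k = 1.645 + 2.326) | 3.97 | 99.0% | 98.0% |
| m = 2.196, SD 2.21 | 4.92 | 99.95% | 99.9% |
| m = 2.196, SD 5.77 (assumption) | 1.885 | 59% | 19% |
| m = 2.196, SD 6.32 (assumption) | 1.72 | 53% | 6% |

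The first row only re-enters the stated power; it is not derived from the plan's mean and SD. The last two rows use the pre-operative standard errors in 8.2. The URS group gives 2.0 × √10 = 6.32 and the ESWL group 0.8 × √50 = 5.66. Pooled: √[(49 × 5.66² + 9 × 6.32²)/58] = 5.77. The plan does not adopt these SDs.

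**3. Keeping 99% for both directions from the first row.** The ratio is (1.645 + 2.576)²/(1.645 + 2.326)² = 1.13, and 49 × 1.13 = 55.4, so 56 per arm. That is 112 in total, and 112/0.90 = 124.4, so 125 enrolled. With SD 2.21 and m = 2.196, 37 per arm is enough, fewer than the 49 planned.

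**4. If the true difference is not zero.** From the first row, at a difference of 10%, 20% or 30% of the margin, two-way power is 97.0%, 93.6% or 87.2%. One-way power in the unfavourable direction is 97.3%, 93.7% or 87.2%, so the gap closes.

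**5. What an unnamed direction permits.** Whenever m exceeds 1.645 standard errors, the laser with the lower observed mean passes against the other. At 49 per arm and m = 2.196, that holds for any SD up to 2.196/[1.645 × √(2/49)] = 6.6 ng/mL. Success in at least one direction is therefore close to guaranteed and says almost nothing about both lasers.

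**The case against.** The strongest reply is that this is a matter of wording. On the plan's own constants, two-way power is 98% or better, so the sample size survives. Passing in one direction is also not in itself a false claim: with a positive margin the two non-inferiority nulls cannot both be true, so trying both directions does not raise the rate of false claims above the nominal 5%. The mismatch between the stated purpose and the Kruskal-Wallis test is the larger fault, and mending it would force a choice of direction anyway. All of this stands. It limits the point to what may be concluded; it does not remove it, because the mismatch cannot be mended until someone says which claim is meant.

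A reader might go further in three ways that the documents do not support.
- **That the plan is really an equivalence trial.** It never says so. An unnamed reference could equally be a one-way comparison left unfinished.
- **That power collapses to 19% or lower.** This needs a pre-operative SD in place of the post-operative 2.21, and one-way power would by then be only 59% to 53%. The SD does most of that damage.
- **That 49 per arm proves a one-sided 5% calculation.** It does not follow from the stated inputs, and an assumed 30% rate at one-sided 2.5% matches it as well.

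**Conclusion.** The point holds as a fault in how the claim and its test are specified. Section 8.2 sets a non-inferiority purpose with no reference laser and no direction, and 8.4.2 plans a test that can show neither non-inferiority nor equivalence. The trial as written cannot deliver its stated conclusion.

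It does not hold as a sample-size fault. Requiring both directions costs about one percentage point if the stated 99% is accepted, and less than 0.1 point at SD 2.21 with a 2.196 ng/mL margin. These figures assume no true difference, one-sided 5% for each comparison, an additive margin of 40% of 5.49, and 49 evaluable patients per arm. They would worsen materially only if the post-operative SD were near 5.8 to 6.3, which is an assumption and would undermine the one-way calculation too.

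**What to change.** In 8.2 and 8.4.2, before any assay is run, choose one claim and write its decision rule.

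- **Equivalence, which fits the plan's description of the lasers as interchangeable.** The 90% confidence interval for the between-laser contrast in post-operative uKIM-1 must lie wholly within two-sided limits derived from the plan's 40%. State the scale. In ng/mL the limits could be ±2.196; as a ratio, 1/1.40 to 1.40. The two are not the same: 1/1.40 = 0.71, a 29% reduction. Restate power for this test on the same scale. The figures above apply to the additive limits only.
- **One direction.** Name the reference laser, reword the purpose to match, and compare a one-sided confidence limit with the margin.

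Either way, state the sidedness of alpha and which post-operative sample is meant, since section 1.3 collects one at one hour and one at 10 days. Say also that a non-significant Kruskal-Wallis test will not be read as evidence of non-inferiority or equivalence.

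The cost is a few sentences and, under equivalence, a slightly less favourable power figure. No additional patients are needed on this ground unless the sponsor insists on 99% for both directions from the stated baseline, which would take about 56 per arm.
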